13.6. Interim Analyses

No interim analysis will be performed.

14. DEFINITIONS, RECORDING, AND REPORTING OF ADVERSE EVENTS

14.1. Definition of Adverse Events

According to International Council for Harmonisation (ICH) guidance E2A, Clinical Safety Data Management: Definitions and Standards for Expedited Reporting, an AE is any untoward medical occurrence in a patient or clinical investigation subject administered a pharmaceutical product and which is not necessarily required to have a causal relationship with this treatment. An AE can therefore be any unfavorable and unintended sign (including an abnormal laboratory finding, for example), symptom, or disease temporally associated with the use of a medicinal product, whether or not considered related to the medicinal product.

A TEAE is an AE that either commenced following initiation of study treatment or was present prior to study treatment but increased in frequency or severity following initiation of study treatment.

14.2. Adverse Event Recording

14.2.1. Coding the Adverse Event

Standard medical terminology should be used in describing AEs. MedDRA® will be used as the standard coding dictionary for AEs and in describing the patient's medical history, and the World Health Organization (WHO) Drug Dictionary will be used to code concomitant medications. Informal descriptions should be avoided.

14.2.2. Severity of Adverse Event

AEs should be graded as mild, moderate, or severe using the following definitions.

- *Mild:* Awareness of signs or symptoms, but easily tolerated and of minor irritant type causing no loss of time from normal activities. Symptoms do not require therapy or a medical evaluation; signs and symptoms are transient.
- *Moderate:* Events introduce a low level of inconvenience or concern to the participant and may interfere with daily activities, but are usually improved by simple therapeutic measures; moderate experiences may cause some interference with functioning.
- **Severe:** Events interrupt the participant's normal daily activities and generally require systemic drug therapy or other treatment; they are usually incapacitating.

To make sure there is no confusion or misunderstanding of the difference between the terms "serious "and "severe," which are not synonymous, the following note of clarification is provided. The term "severe" is often used to describe the intensity (severity) of a specific event (as in mild, moderate, or severe myocardial infarction); the event itself, however, maybe of relatively minor medical significance (such as severe headache). This is not the same as "serious," which is based on patient/event outcome or action criteria usually associated with events that pose a threat to a patient's life or functioning. Seriousness (not severity) serves as a guide for defining regulatory reporting obligations.

14.2.3. Relationship of Adverse Events to Study Drug

The Investigator will assess the potential relationship of the AE to study drug using the following descriptions.

- *Not Related:* This category applies to an AE that is clearly not related to the study drug beyond a reasonable doubt. That is, another cause of the event is most plausible; and/or a clinically plausible temporal sequence is inconsistent with the onset of the event and the administration of study drug and/or a causal relationship is considered biologically implausible.
- *Unlikely Related:* This category applies to an AE that could reasonably be considered caused by something else, and where there is no known or expected response pattern to the suspected study drug.
- *Possibly Related:* This category applies to an AE that follows a reasonable temporal sequence from administration of the study drug and that follows a known or expected response pattern to the suspected study drug, but that could readily have been produced by a number of other factors.

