Any death occurring during the study, during the per-protocol follow-up period, or reported to the Investigator after study participation (no required post-study time limit) must be reported to Tonix or its designee(s) immediately, whether or not it is considered treatment-related. Initial SAE reports must be followed by detailed descriptions. These should include copies of hospital case records and other documents when requested. Telephone and e-mail reports must be confirmed promptly either by facsimile or by email. For reporting SAEs, Tonix's designated Medical Monitor should be called, and the relevant forms submitted to Premier PV within 24 hours of the site's awareness of the SAE. The contact information for the Medical Monitor is as follows:

The Investigator, or the sponsor or designee in the case of a central IRB, also must notify the ethics committee (EC)/IRB of the occurrence of the SAE, in writing, as soon as is practicable and in accordance with local law. A copy of this notification must be provided to Tonix or its designee.

In the event of an SAE that meets the criteria for expedited reporting, an investigational new drug (IND) Safety Report will be prepared for submission to the FDA.

Clinical investigators also have the authority to unblind their own SAE patients if/when the unblinded treatment information could impact the patient's clinical management. There is a module within the Interactive Response Technology system for investigators' use if "emergency" unblinding is required; however, the Investigator is requested to confer with the Medical Monitor before taking any action. The need for emergency unblinding is not expected for this study, in light of the nature of the study drug.

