8.3 Safety Endpoints

To handle missing or partial AE and concomitant medication dates, the following rules will be applied.

For partial start dates:

- 1. If the year is unknown, then do not impute the date but assign a missing value.
- 2. If the month is unknown, then:
 - a. If the year matches the year of the first dose date, then impute the month and day of the first dose date.
 - b. Otherwise, assign "January."
- 3. If the day is unknown, then:
 - a. If the month and year match the month and year of the first dose date, then impute the day of the first dose date.
 - b. Otherwise, assign "01."

For partial end dates:

- 1. If the year is unknown, then do not impute the date but assign a missing value.
- 2. If the month is unknown, then assign "December."
- 3. If the day is unknown, then assign the last day of the month.

Adverse events are categorized as pre-treatment adverse events or treatment-emergent adverse events based on the response to the CRF question "Did the AE start prior to the first dose?"

The missing severity of an AE will be imputed to "severe"; the missing relationship to study drug of an AE will be imputed to "possibly related".

After implementing the rules above, the following strategy will be used to determine whether medications with missing start or stop dates are prior or concomitant medications:

- 1. If the start date and stop date are both missing, then the most conservative approach is taken and the medication is considered to be a concomitant treatment.
- 2. If the start date is missing but the stop date is not missing and is after the day of first study dose administration, then the most conservative approach is taken and the medication is considered to be concomitant.
- 3. If the start date is missing but the stop date is not missing and is on or before the day of first study dose and after the date of signed informed consent, then the medication is considered to be a prior treatment.
- 4. If the start date is not missing but the stop date is missing, then the most conservative

Protocol: TNX-CY-F307 Page 24 of 45

Final v1.0

approach is taken and the medication is considered to be concomitant.

Protocol: TNX-CY-F307 Page 25 of 45

Final v1.0

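### Protocol 14.2.3 gives clear-cut drug reactions no causality category and never lets a new reaction be graded Possibly Related

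*Protocol*

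**What the plan says.** Protocol 14.2.3 opens with the instruction: "The Investigator will assess the potential relationship of the AE to study drug using the following descriptions". Three descriptions follow.

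- **Not Related:** "This category applies to an AE that is clearly not related to the study drug beyond a reasonable doubt". The text explains this by another cause being the most plausible, and/or inconsistent timing, and/or biological implausibility.
- **Unlikely Related:** the event "could reasonably be considered caused by something else, and where there is no known or expected response pattern to the suspected study drug".
- **Possibly Related:** the event has reasonable timing after dosing and "follows a known or expected response pattern to the suspected study drug, but that could readily have been produced by" several other causes.

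Neither document has a higher level such as probable or definite. SAP 8.3 is consistent with Possibly Related being the top of the scale. It imputes missing severity to the worst grade, and in the same sentence "the missing relationship to study drug of an AE will be imputed to" Possibly Related.

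The grades are used in the summaries of TEAEs by relationship and by strongest relationship (Protocol 13.5, SAP 11.1). Neither document gives a rule for an event that meets none of the three descriptions.

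**The concern.** A causality scale should give every event one place, and its top level should hold the events most likely to be caused by the drug. This scale does neither. Its top level requires that the reaction is already known and also that something else could readily explain it. The first condition shuts out new reactions. The second shuts out the most convincing known ones.

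At stake is the meaning of the relationship tables, which form part of the safety evaluation that is the trial's secondary objective. An investigator who follows the text must grade a new reaction low or leave it ungraded. One who ignores the text will probably choose Possibly Related. The tables would then reflect how each site resolved the wording as well as what happened to patients.

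**Working it through.** The plan states no figure to reproduce, so the check is whether the three descriptions cover every kind of event.

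**Inputs, all from Protocol 14.2.3.** Each is yes or no:

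- T: timing is plausible
- K: known or expected response pattern
- A: another cause could reasonably or readily explain the event
- M: another cause is the most plausible one (M implies A)
- B: biologically plausible (K implies B)

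**Definitions as conditions**

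- Not Related = M, or not T, or not B
- Unlikely Related = A and not K
- Possibly Related = T and K and A

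Two choices favour the plan. Any single item in the Not Related list is taken to be enough, and *reasonably* and *readily* are treated as the same test.

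**Number of combinations.** T has 2 values, the pair (A, M) has 3 permitted values and the pair (K, B) has 3, so 2 × 3 × 3 = 18.

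**Implausible timing (9 combinations).** All 9 are Not Related; 4 of them also meet Unlikely Related.

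**Plausible timing (9 combinations)**

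| | Other cause most plausible | Other cause reasonable, not most plausible | No other cause |
|---|---|---|---|
| Known pattern | Not and Possibly | Possibly | **none** |
| No known pattern, biologically plausible | Not and Unlikely | Unlikely | **none** |
| No known pattern, biologically implausible | Not and Unlikely | Not and Unlikely | Not |

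**Results**

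- 2 of 18 fit no category: the clear-cut known reaction, and the new reaction with no other cause.
- The second row never reaches Possibly Related. A new, biologically plausible reaction with a reasonable but not leading alternative fits Unlikely Related only.
- 8 of 18 fit two categories (4 in the table, 4 with implausible timing). In one of these, an event with a known pattern whose most plausible cause is something else meets both the bottom and the top level.
- The remaining 8 fit exactly one: 2 + 8 + 8 = 18.

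**Sensitivity.** If *readily* is a stricter test than *reasonably*, the gap widens. A known reaction with a reasonable but not ready alternative then fails Possibly Related on the alternative-cause condition and fails Unlikely Related because its pattern is known.

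**Comparison with SAP 8.3.** A new reaction with a reasonable alternative cause is Unlikely Related when graded by the protocol text, but Possibly Related when the field is left blank. Following the definition gives a less conservative entry than skipping it.

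**The case against.** The last clause of Possibly Related can be read as a concession about limited certainty and not as an entry test. That is a fair reading, and it would bring clear-cut known reactions into the top level. The documents do not state it, however, and it does nothing for new reactions, because the known-pattern condition remains.

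The unclassifiable cases may also be uncommon. Fibromyalgia symptoms fluctuate (Protocol 12.3.1), many concomitant drugs are allowed (9.1), and the appended AMRIX label lists a very broad range of reactions. This stands as a limit on frequency. It is weaker for local oral effects after dosing, such as numbness, tingling or taste, which the protocol anticipates (12.3.2) and which often have little competing explanation. A CRF completion guide might supply a default, but none is among the documents.

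A reader might infer three stronger things that the documents do not support.

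- **Unexpected serious reactions would escape expedited review.** Protocol 14.3 requires every SAE to be reported with no causality condition, and deaths whether or not thought related. The IND safety report is prepared "In the event of an SAE that meets the criteria for expedited reporting", and those criteria are neither given nor tied to the 14.2.3 category.
- **Events would disappear from the tables.** An Unlikely Related event still appears in the relationship summaries. New-onset events enter the all-TEAE tables whatever their grade, and oral AEs are identified by a CRF question that does not ask about cause (SAP 11.1.3). The comparison of TEAE rates between arms needs no causality grade. Relationship does enter one clause of the SAP 11.1 TEAE definition, for worsening of pre-existing events, but greater severity or frequency also qualifies those.
- **Any conceivable alternative cause forces Unlikely Related.** The text requires that the event could reasonably be attributed to something else, which is a higher bar.

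**Conclusion.** The point holds as a defect in a stated rule. As written, the scale has no place for a well-timed known reaction without a ready alternative cause. It places a well-timed new reaction at Unlikely Related at best when another cause is reasonable, and nowhere when none is.

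The size is modest. The damage is confined to misclassified or inconsistently classified entries in descriptive relationship tables; no efficacy endpoint, formal test or stated SAE reporting duty is touched. The figure of 2 in 18 counts logical cases and says nothing about how many events are affected. The documents give no rate from which to estimate that.

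The conclusion assumes that the conditions in each description are joint, as the grammar suggests, and that no unseen site instruction overrides them.

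**What to change.** Amend Protocol 14.2.3 so that the levels are exhaustive and do not overlap, and say that they are applied in this order:

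1. **Not Related:** drug causation is excluded beyond reasonable doubt, because timing is inconsistent, the link is biologically implausible, or another cause is clearly established.
2. **Unlikely Related:** another cause is more likely, but study drug cannot be ruled out. Remove the known-pattern criterion.
3. **Possibly Related:** timing is reasonable and there is a reasonable possibility that study drug caused the event, whether or not the reaction is already known and whether or not other causes exist.

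Both unclassified cases above then fall in Possibly Related. Keeping *clearly established* for Not Related and *more likely* for Unlikely Related stops those two levels from merging. Expectedness can be judged separately by the sponsor. SAP 8.3 needs no change.

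The cost is a short amendment with EC/IRB approval before it takes effect (Protocol 15.1), a notice to sites, and somewhat more AEs classed as possibly related. If the change is made mid-study, AEs already graded under the present wording need re-review while still blinded, or flagging, so that the tables do not silently mix two scales.

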14.3. Serious Adverse Events (SAEs) and Serious Adverse Drug Reactions

Any SAE that occurs at any time during the study, including a clinically significantly abnormal laboratory test result that is considered serious, must be reported to Tonix or its designee(s) so that Tonix may comply with regulatory obligations. If the SAE is life-threatening or fatal, it must be reported to Tonix or its designee(s) immediately, by facsimile and telephone. For these and all other SAEs, an SAE report form must be completed and sent by facsimile or email to Tonix or its designee(s) within 1 working day of the site's initial awareness of the event. These requirements apply equally to all patients, regardless of the study phase or the at-risk patient's treatment assignment or dosage.

[figure not shown]
A serious adverse event (experience) or reaction is any untoward medical occurrence that, at any dose:

- Results in death,
- Is life-threatening,
- Requires in-patient hospitalization or prolongation of existing hospitalization,
- Results in persistent or significant disability/incapacity,
- Is a congenital anomaly/birth defect, or
- Is an important medical event

NOTE: The term "life-threatening" in the definition of "serious" refers to an event in which the patient was at risk of death at the time of the event. It does not refer to an event that hypothetically might have caused death if it were more severe.

Medical and scientific judgment should be exercised in deciding whether expedited reporting is appropriate in other situations, such as important medical events that may not be immediately life-threatening or result in death or hospitalization but may jeopardize the patient or may require intervention to prevent one of the other outcomes listed in the definition above. *These should also usually be considered serious*. Examples of such events are intensive treatment in an emergency room or at home for allergic bronchospasm, blood dyscrasias or convulsions that do not result in hospitalization, or development of drug dependency or drug abuse. The development of C-SSRS suicidal ideation type 4 (intent) or type 5 (specific plan and intent) any time after consenting to the study should always be reported as an SAE. Additionally, since only Types 1 and 2 are allowed at Screening or Baseline, the development of C-SSRS type 3 (method but no plan or intent) after consenting should always be reported as an AE.

Any death occurring during the study, during the per-protocol follow-up period, or reported to the Investigator after study participation (no required post-study time limit) must be reported to Tonix or its designee(s) immediately, whether or not it is considered treatment-related. Initial SAE reports must be followed by detailed descriptions. These should include copies of hospital case records and other documents when requested. Telephone and e-mail reports must be confirmed promptly either by facsimile or by email. For reporting SAEs, Tonix's designated Medical Monitor should be called, and the relevant forms submitted to Premier PV within 24 hours of the site's awareness of the SAE. The contact information for the Medical Monitor is as follows:

The Investigator, or the sponsor or designee in the case of a central IRB, also must notify the ethics committee (EC)/IRB of the occurrence of the SAE, in writing, as soon as is practicable and in accordance with local law. A copy of this notification must be provided to Tonix or its designee.

In the event of an SAE that meets the criteria for expedited reporting, an investigational new drug (IND) Safety Report will be prepared for submission to the FDA.

Clinical investigators also have the authority to unblind their own SAE patients if/when the unblinded treatment information could impact the patient's clinical management. There is a module within the Interactive Response Technology system for investigators' use if "emergency" unblinding is required; however, the Investigator is requested to confer with the Medical Monitor before taking any action. The need for emergency unblinding is not expected for this study, in light of the nature of the study drug.

14.4. Pregnancy

The active pharmaceutical product in TNX-102 SL is cyclobenzaprine HCl, which is in Pregnancy Category B (See Appendix 2 for AMRIX® Package Insert). All pregnancies occurring during the study (after exposure to study drug) or within 28 days after discontinuation of study drug must be followed until resolution (i.e., birth or voluntary or spontaneous termination of the pregnancy). All women of childbearing potential are therefore required to continue contraception for 28 days after study drug discontinuation. Any patient found to be pregnant at any time during the study will be withdrawn from the study immediately. Any pregnancy outcome that meets the criteria for an SAE will be reported as an SAE.

15. PROCEDURES FOR MODIFYING THE PROTOCOL OR TERMINATING THE STUDY

15.1. Protocol Modifications and Deviations

The Investigator will make all reasonable efforts to comply with the written protocol and protocol amendments. All protocol modifications must be reviewed and approved by the appropriate EC/IRB before the revised protocol can be implemented. Emergency revisions that eliminate an apparent hazard to patients do not require preapproval by the EC/IRB. However, the EC/IRB must be notified, in writing, as soon as possible after the modification has been made. A copy of this communication must be forwarded to Tonix.

15.2. Study Termination

The study may be prematurely terminated at any time at the discretion of Tonix, its designee, or the Principal Investigator. Should premature termination be considered necessary, written notification documenting the reason for study termination will be provided, and specific procedures for termination will be arranged. Circumstances that may warrant premature study termination include, but are not limited to, the following.

- Determination of unexpected, significant, or unacceptable risk to patients
- Failure to enter patients at an acceptable rate
- Insufficient adherence to the requirements of the protocol
- Insufficient provision of complete and evaluable data
- Plans to modify, suspend, or discontinue development of the study drug

In the event that the study is terminated prematurely, all study materials must be returned to Tonix or its designee.

16. ETHICAL CONSIDERATIONS

16.1. Ethical Conduct of the Study

This protocol is written in accordance with the principles established by the 18th World Medical Assembly General Assembly (Helsinki, 1964) and amendments and clarifications adopted by subsequent General Assemblies. The Investigator will make sure that the study described in this protocol is conducted in full conformance with those principles, the protocol, current FDA regulations, ICH Good Clinical Practices (GCP) guidelines, Good Laboratory Practices (GLP) guidelines, local ethical and regulatory requirements, including the Federal Food, Drug and Cosmetic Act, US applicable Code of Federal Regulations (title 21), any EC requirements relative to clinical studies. As required by the US FDA, the study drug may not be shipped to any participating Investigator until the requisite study documentation has been submitted to the IND.

Should a conflict arise, the Investigator will follow whichever law or guideline affords the greater protection to the individual patient. The Investigator will also make sure he or she is thoroughly familiar with the appropriate administration and potential risks of administration of the study drug, as described in this protocol and the Investigator's Brochure, prior to the initiation of the study.

